#### **2.3.2.3 Hypoglycemia:**

Propranolol has been reported to cause hypoglycemia in infants treated with propranolol. While these data is not established in old patients, all study patients will be encouraged to keep a regular food schedule and snack if they feel fatigued or dizzy.

If patients become ill for other reasons during the study period (eg URIs, gastroenteritis) during the study period, they are encouraged to contact us. Their propranolol dose will be held until they are able to tolerate POs.

#### **2.3.2.4 Bronchospasm:**

Patients will be monitored for respiratory symptoms such as coughing, wheezing, or shortness of breath.

#### **2.3.2 Pharmacology/Pharmacokinetics/Correlative Biological Studies**

Propranolol is well absorbed after oral administration. It is lipophilic and subject to significant first-pass hepatic metabolism so that only approximately 25% of propranolol reaches the systemic circulation. Peak blood levels occur at about 1-4 hours after an oral dose. Multiple metabolic pathways are involved in propranolol elimination (including those in the cytochrome P450 system).

### **2.4 Overview of Proposed Lymphedema Study**

After patients have been registered, screened, and consented (Eligibility Screening Worksheet, Registration Form Consent form, HIPAA authorization form, Appendix 1), they will be entered into the study. Propranolol as a single agent will be administered orally, equally divided, two times a day (BID). Patients may receive up to 8-weeks of therapy in the absence of progressive disease or unacceptable toxicity. Treatment response will be assessed by patient self-reported symptoms and questionnaires (Appendix 2), physical exam, and radiographically by MRI.

The starting dose of propranolol will be 0.5 mg/kg/day, which is the current institutional dose for initial treatment for cardiovascular and hemangioma indications in children. Patients will be weighed and their weight will be rounded to the closest 10kg (eg 50-54kg = 50kg, 55-59 = 60kg).

**Table 1**

**Table 1. Propranolol intra-patient dose escalation schedule and assessments**

	Propranolol	Assessments		
		Subjective	Objective	Other
Week 1 (initiation)	0.5 mg/kg/day, divided bid	Entrance Interview Quality of Life Questionnaire	Physical Exam, Imaging	Blood Draw, a Tissue Biopsy a
Week 2	1 mg/kg/day, divided bid a,b	Quality of Life Questionnaire	Physical Exam	
Week 4	2 mg/kg/day, divided bid a,b	Quality of Life Questionnaire	Physical Exam	Blood Draw
Week 6	3 mg/kg/day, divided bid a,b	Quality of Life Questionnaire	Physical Exam	
Week 8	3 mg/kg/day, divided bid a,b	Exit Interview, Quality of Life Questionnaire	Physical Exam, Imaging	Blood Draw, a Tissue Biopsy a

aWeight rounded to the nearest 10-kg increment

bDose escalation in the absence of clinical contraindications.

bIn the presence of clinical contra-indications, the patients will remain on their current level of dosage, or decreased to the previous level, or have their medications held.

A maximum of 8-weeks of therapy may be administered

Studies have shown that the peak effect of oral propranolol on blood pressure and heart rate occurs 1 to 3 hours after it is taken. As such, current recommendations are that patients should have HR and BP done at baseline and also hourly for the first 2 hours after a dose increase, and at least once after the target dose is achieved. As dose response is generally most significant after the first dose, once normal vitals are obtained with the first dose there is no recommendation that vitals should be re-checked at the same dose level, unless the patient is very young, has cardiovascular issues or co-morbidities, or if clinical complaints arise.

Patients must have vitals within the normal range for their age group prior to starting in the study. After the first dose (0.5mg/kg/day), they will be re-evaluated. If their heart rate (HR) and blood pressure (BP) are within normal limits (WNL), they will continue on this dose for the next week until the next evaluation. If there is a fall below normal range (>15%) of HR and BP, they will rest off medications for 2 weeks and re-challenged. If they tolerate the dose, they will continue on the study. If they cannot tolerate the lowest dose for the 2nd time, they will be removed from the study, as they cannot tolerate the lowest dose.

At the 2nd-week re-evaluation, they will be escalated to the new dose (1mg/kg/day) if the baselines HR and BP are WNL. Patients will have HR and BP noted after first new dose (1mg/kg/day) of propranolol to ensure that the propranolol is tolerated. If the HR and BP are WNL, they will continue on this new dose and re-evaluated in 2 weeks for the 4th-week evaluation. If they have a drop in HR and BP to below normal range, they will be de-escalated and remain on the prior dose (0.5mg/kg/day) until the next visit (week 4).

At the 4th and 6th-week evaluation, their baseline vitals will be evaluated and their propranolol escalated to the next dose (if vitals are WNL) and have their HR and BP assessed after first new dose. Propranolol will stay increased or held at old dose depending on HR and BP after the first new dose as described above. If on re-evaluation in 2 weeks a patient continues to have below normal HR and blood pressure on re-challenge of the escalated dose, they will not be escalated and remain at the last tolerated dose for the remainder of the 8 week period with no further re-challenges. For patients with below normal HR and BP and needed their doses held, they will be reported as AEs.

At each study visit, patients will be asked to complete validated questionnaire to assess for tolerance to propranolol treatment, subjective changes in lymphedema symptoms, and self-reported function and activities of daily living (SF-36, LYMPH—ICF, and LYMPH—ICF—LL) (See attached documents, Appendix 2). Physical examination will include weight and BMI, vitals (HR, BP), and measurement of girth of normal and affected extremity.

MRIs and blood tests will be performed at study entry and study endpoint to assess for changes in lymphedema tissue composition[21-23] in response to propranolol.

Blood draws will be performed at study entry, at the midpoint, and study endpoint to assess for changes in circulating biomarkers in response to propranolol treatment.

Correlative biomarkers assessed will include markers of progenitor, endothelial, lymphatic, macrophage, and adipocyte cells, and expression of beta-adrenergic receptors (Table 3).

Patients will also receive punch biopsies at study entry and at study endpoint to assess for expression of biomarkers. Genetic studies will be performed from tissues obtained at study entry to evaluate for presence of PIK3CA mutation[36, 37] and correlated to response to propranolol. Genomic data generated will be deposited into an NIH database per NIH regulations (de-identified).

In the context of this study, we will perform immunohistochemical analyses on biopsied tissues to assess alterations in lymphatic vessel/channel formation, and changes in inflammation (Table 3). We have selected markers that we have previously shown to be altered by propranolol either in isolated LMPCs in culture or in the mouse model. Expression of the beta-adrenergic receptors will be assessed, as propranolol is a pan-beta-adrenergic receptor antagonist. To date, no tissue nor circulating molecular markers have been identified to correlate with LM patient improvement. Identification of such markers could provide an important benefit to affected patients. Morphological changes in the lymphatic vasculature will also be quantified using ImageJ software. Student's T-test will be employed to determine significance, with  $p < 0.05$  considered significant.

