### 2.3.2 Risk Assessment

#### 2.3.2.1 Hypotension and Bradycardia:

Studies have shown that the peak effect of oral propranolol on blood pressure and heart rate occurs 1 to 3 hours after it is taken[28, 29]. As such, current recommendations are that patients should have HR and BP done at baseline and also hourly for the first 2 hours after a dose increase, and at least once after the target dose is achieved. As dose response is generally most significant after the first dose, once normal vitals are obtained with the first dose there is no recommendation that vitals should be re-checked at the same dose level, unless the patient is very young, has cardiovascular issues or co-morbidities, or if clinical complaints arise.

Pediatric patients must have vitals within the normal range for their age group, and adults with normal established vitals, prior to starting a dose. Dose escalations will take

place as given in the table above. Patient must have no evidence of clinical contraindications with acceptable HR and BP parameters prior to dose escalation occurring. If individuals are found to have a fall in their blood pressure or heart rate outside of normal range, they will have dose de-escalation to the prior tolerated dose level. If they are able to tolerate this lower dose level with normal parameters and no clinical symptomatology they will have a re-challenge of the dose escalation after 2 weeks. If on re-escalation they once again have fall in HR and blood pressure, they will again undergo dose de-escalation to the prior tolerated dose level for 2 weeks and re-evaluated again until the end of the 8-week study. If the patients are already at the lowest doses, they will be given a 2-week rest and re-evaluated after 2 weeks. If HR and BP then fall within normal parameters they will be reintroduced to the study at the lowest study dose of propranolol. If patient is once again found to have fall in HR/BP below normal parameters for age upon an attempt to re-start propranolol, they will be removed from the study. That is, all patients who do not tolerate a dose increase for the 2nd time will be held at the last tolerated dose until the end of the study. If a patient cannot tolerate the lowest doses twice, they will be removed from the study.

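### The vital-sign trigger for a failed escalated dose is worded *or* in some rules and *and* in others, so a patient with one low sign has no single rule

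*Combined protocol and SAP*

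**What the plan says.** The plan does not define a failed dose in one place. It restates the vital-sign trigger wherever it is used.

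- **Section 2.3.2.1.** The step-back rule opens "If individuals are found to have a fall in their blood pressure or heart rate outside of normal range". The rule for the next challenge opens "If on re-escalation they once again have fall in HR and blood pressure". The rule for restarting at the lowest dose opens "If patient is once again found to have fall in HR/BP below normal parameters for age upon an attempt to re-start propranolol".
- **Section 2.4.** At the first 0.5 mg/kg/day dose: "If there is a fall below normal range (>15%) of HR and BP, they will rest off medications for 2 weeks". At 1 mg/kg/day the continue branch is "If the HR and BP are WNL, they will continue on this new dose" and the fail branch is "If they have a drop in HR and BP to below normal range"; weeks 4 and 6 refer back to these. Escalation ends for a patient who "continues to have below normal HR and blood pressure on re-challenge of the escalated dose". On reporting: "For patients with below normal HR and BP and needed their doses held, they will be reported as AEs".
- **Section 5.2.2.** Two hours after an escalated dose, and again at the return visit, a fall in either sign is enough. The patient goes home on the new dose only if both signs are normal. There is no separate re-challenge trigger. At initiation the signs are joined by *and*; at re-initiation the text is HR/BP.
- **Section 6.1.1.1.** The opening rule, for asymptomatic patients, needs either sign. Item c, for symptomatic patients, needs both. Item e, for patients on 0.5 mg/kg/day at 4 weeks, needs either.
- **Table 5.** The rows for values below normal do not say how many signs must be low. The symptomatic row uses HR/BP for the 0.5 mg/kg/day dose.
- **Section 14.2.3.** Two failed challenges at 1 mg/kg/day lead to removal. What counts as failed on HR or BP is not stated.

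**The concern.** The trigger decides whether a beta-blocker increase is kept, stepped back or held, and whether a second failure ends escalation or, at 1 mg/kg/day, ends participation. In section 11.2.2 the primary endpoint is tolerability of the escalating dose, with vital signs as its objective component. Section 8.4 reports toxicity rates dose by dose and evaluates response at the highest tolerable dose. A patient stopped after two failures is never challenged at the next level, so the trigger affects who contributes at each dose. If staff resolve the wording differently from one patient to the next, part of the difference in dose reached will reflect how the rule was read rather than how the drug was tolerated.

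**Working it through.** The plan gives no figure to reproduce here. The check is a comparison of wording, followed by a look at scale.

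**1. Count of the trigger wordings.**

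- *Or*: 2.3.2.1 first fall; 5.2.2 two-hour check; 5.2.2 return visit; 6.1.1.1 opening rule; 6.1.1.1e. Total 5.
- *And*: 2.3.2.1 re-escalation; 2.4 first dose; 2.4 at 1 mg/kg/day; 2.4 re-challenge; 5.2.2 initiation; 6.1.1.1c. Total 6.
- *HR/BP*: 2.3.2.1 restart; 5.2.2 re-initiation; Table 5 at 0.5 mg/kg/day. Total 3.

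5 + 6 + 3 = 14. The adverse-event sentence in 2.4 is a further *and*. These are 14 statements, not 14 conflicts, because several concern different events.

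**2. The same statements sorted by event.**

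| Event | 2.3.2.1 | 2.4 | 5.2.2 | 6.1.1.1 and Table 5 |
|---|---|---|---|---|
| First failure, escalated dose | *or* | *and* | *or* | *or* if asymptomatic; Table 5 does not specify |
| Re-challenge, escalated dose | *and* | *and* | none separate; its two-hour *or* on an ordinary reading | none separate |
| Symptomatic patient | none separate | none separate | none separate | *and* (item c); Table 5 does not specify |
| First 0.5 mg/kg/day dose | no trigger of its own | *and*, >15% | *and*, no margin | none |
| Second attempt at 0.5 mg/kg/day | HR/BP | no sign named | HR/BP | HR/BP (Table 5, symptomatic row) |
| Still on 0.5 mg/kg/day at week 4 | none | none | none | *or* (item e) |

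The plain same-event conflict is in the first row. The second row shows 2.3.2.1 changing from *or* to *and* between first and second failure. The third shows a symptomatic hold that is harder to trigger, as worded, than the asymptomatic rule above it.

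**3. A patient with low HR and normal BP.**

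- After the first 1 mg/kg/day dose: 2.3.2.1 steps the patient back; 5.2.2 returns the patient to the earlier dose; in 2.4 the continue branch is not met (HR is low) and the fail branch is not met (BP is normal).
- Same finding two weeks later: the second-failure wording in 2.3.2.1 and 2.4 is not met, although the two-hour check in 5.2.2 would be.
- Same finding with symptoms: the 6.1.1.1 opening rule is limited to asymptomatic patients, and item c needs both signs. The Table 5 symptomatic row would ordinarily cover this patient but does not say so.

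**4. How far the wordings differ.** There are three abnormal patterns: HR only, BP only, both. *Or* is met by 3 and *and* by 1, so they differ on 3 − 1 = 2.

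**5. Scale.** Let h be the proportion with low HR, b with low BP and x with both. The wordings differ for h + b − 2x. The documents give none of these for this population, so the following are illustrations.

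- Table 7 rates (asymptomatic events in infantile hemangioma): b = 2.8%, h = 0.9%, x anywhere from 0 to 0.9%. The result is 3.7 − 1.8 = 1.9% up to 3.7%. In 20 patients: 20 × 0.019 = 0.38 to 20 × 0.037 = 0.74.
- Assumed 10% each, independent: 0.10 + 0.10 − 2 × 0.01 = 18%; 20 × 0.18 = 3.6 patients.
- Assumed 20% each, independent: 0.20 + 0.20 − 2 × 0.04 = 32%; 20 × 0.32 = 6.4 patients.

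The result runs from under one patient to about six, depending entirely on the assumption.

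**The case against.** The best defence is that the author uses the phrases as synonyms. The second-failure sentence in 2.3.2.1 speaks of the fall happening once again, which points back to the *or* rule before it, and 5.2.2 moves from *and* to HR/BP for what is plainly the same finding. Section 5.2.2 is the treatment section, while 2.4 is an overview. Of the 14 statements, sections 5 and 6 hold 4 *or*, 2 *and* and 2 HR/BP; four of the six *and* statements are in section 2. Before any escalation the signs must be normal or acceptable. Staff may well apply *or*.

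Much of this stands, and it rules out several stronger readings that a reader might infer:

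- *That 2.4 passes a patient with one low sign.* It does not. Its continue branch needs both signs normal, so the patient is unassigned. No section expressly lets such a patient keep a newly given escalated dose.
- *That the sections contradict each other at the first 0.5 mg/kg/day dose.* Sections 2.4 and 5.2.2 agree on *and* there, and 6.1.1.1e concerns a later event. What remains is the unassigned patient and the margin that appears only in 2.4.
- *That one low sign goes unreported.* Section 13 requires adverse events of every grade to be reported, whatever the 2.4 sentence says.
- *That the response analysis loses patients.* Section 11.5 keeps every eligible treated patient in the main response analysis.
- *That the effect is 5.0 to 6.7 percentage points.* Those are 1/20 and 1/15, the weight of any one patient at the planned 15–20. The plan defines no tolerability proportion based on failed challenges.

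The defence does not remove the conflict. No passage says which wording governs, and 2.3.2.1 and 6.1.1.1 each use both wordings in neighbouring rules, so preferring the treatment section over the overview does not settle the matter.

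**Conclusion.** The point holds for escalated doses and for the symptomatic hold. First failure is *or* in 2.3.2.1 and 5.2.2 but *and* in 2.4; re-challenge is *and* in 2.3.2.1 and 2.4; 6.1.1.1c needs both signs where the asymptomatic rule needs one. This is conflicting wording of a dose-decision rule, not the absence of one. At initiation the issue is narrower: the sections agree, but one low sign is unassigned and the margin is undefined.

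The conclusion rests on a literal reading and on nothing in the documents ranking the sections. The both-normal continue rule suggests that *or* is intended. The number of patients affected cannot be estimated from the documents, and the illustrations above should not be quoted as estimates. The correction is still worth making, because the rule governs dose in a trial whose primary endpoint is tolerability.

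**What to change.** Define the trigger once, in 6.1.1: HR or BP below the age-specific lower limit of normal. Section 4.1.7.4 points to Appendix 7 for normal ranges; that appendix is not in the text available here, so confirm that it covers adults as well as adolescents. This definition is the complement of the existing both-normal continue rule. Refer to it:

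- for first failure and re-challenge at escalated doses in 2.3.2.1, 2.4 and 5.2.2;
- for the symptomatic hold in 6.1.1.1c and Table 5;
- in the 2.4 adverse-event sentence;
- for the meaning of failed, on HR or BP, in 14.2.3.

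For the 0.5 mg/kg/day initiation dose, the sponsor should state one rule in 2.4 and 5.2.2, preferably the same *or* trigger. The 15% margin should be dropped, or given a reference value and used in both sections. These are clinical choices. An *or* rule at initiation would take a patient with one mildly low sign off drug for 1 week (5.2.2) or 2 weeks (2.4) of an 8-week study, with removal after a second failure.

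The cost is a wording amendment, with no added visits or measurements and no change to the 11.2.2 endpoint. The downside is somewhat more patients held or counted as intolerant than under an *and* rule.

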### 1.2 Secondary Aims

- 1.2.1 to assess disease-specific lymphedema patients’ response to propranolol
- 1.2.1a to assess *subjective* patient-reported lymphedema-related symptoms
  - i) Validated questionnaires: LYMPH—ICF, LYMPH—ICF--LL
- 1.2.1b to assess *objective* measures
  - i) Physical examination: Weight, BMI, limb girth discrepancy
  - ii) Imaging evaluation: MRI
  - iii) Blood and tissue analysis: circulating and tissue biomarkers
  - iv) Genetic analysis: correlation of somatic mutations to propranolol response

Table 2. Primary and secondary endpoints

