## 11.2 Study Design/ Endpoints (Table 2)

11.2.1 **Study design:** Each patient will serve as his/her own control, for comparison of study questionnaires (subjective) and with changes in the clinical measurements and imaging measurements of the anatomic area affected by lymphatic malformation compared before and after treatment (objective). In our experience, children exhibiting responses to propranolol displayed these within 2 weeks of beginning propranolol treatment, with estimated reduction in the overall volume of the affected area exceeding 20%.

11.2.2 **Primary endpoints:** The primary endpoint will be the tolerability of escalating dosage of propranolol both by subjective reporting (survey instrument) as well as objective measurements of vital signs. Survey instruments include a general quality of life (QOL) and function survey (SF-36), as well as validated survey instruments for patients with lymphedema (LYMPH—ICF, LYMPH—LCF—LL)[38, 39].

11.2.3 **Secondary endpoints:** The secondary endpoints of the study will be both subjective and objective evaluation of the lymphedema after propranolol treatment, as measured by both survey instrument and objective measurements (clinical exam and radiological studies), as well as biological assays from tissues obtained from biopsies.

11.2.3.1 We will determine whether higher doses of propranolol are well tolerated in this patient population. Secondarily, we will measure determine whether higher doses correlate with improvement in lymphedema symptoms and signs, and healing or improvement of skin lesions, if present (reduced lymphatic leakage, reduced bleeding). Skin lesions will be photographed at clinical visits, and daily lymphatic fluid losses estimated by weight measurements.

Using MRI and body composition analysis, we will determine whether propranolol decreases lymphedema, alters edema water content and location (intracellular vs. interstitial), or alters adiposity of affected extremity.

We will study the biologic activity of oral propranolol against lymphedema, by examining the expression of progenitor cell markers, lymphatic endothelial cell markers, beta-adrenergic receptor expression, macrophage markers and detection of adipocyte content of biopsy specimens (see table below). Results will be compared to ultrasound and magnetic imaging data.

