#### 11.3.2 Imaging Studies

Lymphedema MRI characteristics before and after propranolol therapy will be assessed and related to clinical outcome, as applicable. Specifically, whole body MRI will be used to evaluate body composition and changes in regional adipose tissue depots in the affected limb[21-23].

Furthermore, changes in body composition (water and fat content) in response to propranolol treatment will be evaluated in this study. To evaluate water content, the standard deuterium dilution technique will be used. Fasting patients will have blood draw before drinking stable deuterium isotopes and sodium bromide and after isotope equilibration (about 3-4 hours). Total body water, extra-cellular and intracellular water content can be calculated[22, 40]. Furthermore, a quantitative magnetic resonance (QMR) system will be used to evaluate body (fat and water) content in response to propranolol treatment[21]. Quantification and analysis of results will be performed by [name].

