#### 12.3 **Methods for Evaluation of Measurable Disease**

All measurements should be taken and recorded in metric notation using a ruler, measuring tape, or calipers. All baseline evaluations should be performed as closely as possible to the beginning of treatment.

The same method of assessment and the same technique should be used to characterize

each identified and reported lesion at baseline and during follow-up.

Clinical lesions: The circumference of the affected (vs. unaffected) extremity will be documented in the patient's clinical chart along pre-determined landmarks), as this is a standard part of care for patients with extremity LM. Landmarks include: midway point between ASIS (anterior superior iliac spine) to the patella for the thigh, and midway point between patella to the medial malleolus for lower extremities. The midway point between the axillary crease to medial epicondyle (upper arm) and midway point between medial epicondyle to hamate bone of the wrist (forearm) for upper extremities.

MRI and QMR have excellent contrast, spatial, and temporal resolution. The same scanner should be used and the image acquisition protocol should be followed as closely as possible to prior scans. While CT scans may give even improved spatial resolution, MRI has the advantage of no ionizing radiation, gives superior soft tissue resolution, and allows for multi-planar imaging.

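### The limb-level MRI outcome is an uncontrolled before-after change in the affected limb; the unaffected limb, which the whole-body scan should also show, is not used as a reference.

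*Combined protocol and SAP*

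**What the plan says.** Section 2.4, in the text after Table 1, sets the timing: "MRIs and blood tests will be performed at study entry and study endpoint to assess for changes in lymphedema tissue composition". That sentence names no limb. The region is given elsewhere. Section 11.2.1 makes each patient his or her own control, with "imaging measurements of the anatomic area affected by lymphatic malformation compared before and after treatment". Section 11.3.2 states that "whole body MRI will be used to evaluate body composition and changes in regional adipose tissue depots in the affected limb", and section 11.2.3.1 asks whether propranolol changes edema or "or alters adiposity of affected extremity". Section 8.4 tests changes from baseline with a two-sided t-test or a Wilcoxon test at 0.05.

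For girth, the plan does use the other limb. Section 1.2.1b lists "limb girth discrepancy", section 2.4 calls for "measurement of girth of normal and affected extremity", and section 12.3 says "The circumference of the affected (vs. unaffected) extremity will be documented".

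Three provisions bear on shared change. Section 12.3 says "The same scanner should be used and the image acquisition protocol should be followed as closely as possible to prior scans". Table 6 schedules QMR and the body water evaluation before treatment and at Week 8, and section 11.3.2 describes these as measures of body water and fat. Table 6 also has weight taken at every study visit.

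**The concern.** The drug is systemic, its dose rises over 8 weeks, and the trial itself asks whether it alters body water and fat. Patients are eligible from age 12, so some may still be growing. Any of these influences, or a small change in scanner performance, could move the MRI measurement in both limbs. With no control arm, a before-after test on the affected limb responds to such a change just as it responds to a change in the lymphedema.

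The plan accepts the principle of an internal reference for girth but not for MRI, its radiological measure of response (section 12.4). Sections 1.1.1 and 11.3.2 describe the scan as whole-body, so in a patient with one affected limb the other limb should be in the same images at both times. At stake is whether a significant MRI change can be described as a change in the diseased limb rather than in the patient as a whole.

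**Working it through.** **Inputs from the documents.** Enrollment is 15-20 over 24 months (section 11.1). The accrual rate of 8-10 per year over two years gives 2 × 8 = 16 to 2 × 10 = 20, which agrees with that range apart from one patient at the lower end. The test is a two-sided t-test on change from baseline at 0.05 (section 8.4). The plan states no SD, effect size or power for any MRI measure, so there is no MRI figure to reproduce.

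**Assumed.** The true limb-specific effect is zero, and both limbs shift by a common amount s, in units of the SD of the affected-limb change. Every patient has both scans. The values of s are a range for illustration, not estimates.

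**Step 1: planned test, affected limb only.** The statistic follows a noncentral t with n − 1 degrees of freedom and noncentrality s√n. The critical value is 2.093 for n=20 and 2.145 for n=15.

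| Shift s | n=20: s√n | n=20: rejects | n=15: s√n | n=15: rejects |
|---|---|---|---|---|
| 0 | 0 | 5% | 0 | 5% |
| 0.2 | 0.89 | 13.6% | 0.77 | 11.2% |
| 0.3 | 1.34 | 24.7% | 1.16 | 19.2% |
| 0.5 | 2.24 | 56.5% | 1.94 | 43.8% |

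The last n=20 entry is 56.45% before rounding, hence 56% in whole numbers.

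**Step 2: affected minus unaffected, equal absolute shift.** The shift cancels. A simulation with 40,000 replicates, s = 0.5 and equal SDs gave rejection rates of 4.8-5.1% for correlations of 0.3-0.7 at n=15 and n=20.

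**Step 3: unequal shift.** Suppose the unaffected limb's change has SD ratio r to the affected limb's, its shift scales with that SD, and nothing else is shared. The standardised residual shift is s(1 − r)/√(1 + r²). For s = 0.5 and n=20:

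- r = 0.25: 0.375/1.031 = 0.364, and the test rejects in 34% of trials.
- r = 0.5: 0.25/1.118 = 0.224, and the test rejects in 16% of trials.

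Both are below 56%, and both are above 5%.

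**Step 4: precision.** Interval width relative to the affected limb alone, at the same n:

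- Unequal SDs, nothing shared: √(1 + r²), which is 1.03 at r = 0.25 and 1.12 at r = 0.5.
- Equal SDs, correlation ρ: √(2(1 − ρ)), which is 1.41 at ρ = 0, 1.18 at 0.3, 1.00 at 0.5 and 0.77 at 0.7.

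With equal SDs, the contrast gains precision only when ρ exceeds 0.5.

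**The case against.** The plan is not blind to systemic change. Deuterium and bromide dilution, QMR, weight and whole-body MRI composition would show a general fluid or fat change beside the limb result, and the same-scanner provision limits drift. This stands: the opposite limb is not the only available check. But no section links these measures to the limb analysis, and a whole-body total does not show where a change occurred.

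A reader might infer that the plan counts systemic change as a lymphedema response. The documents do not support that. Section 12.4 defines no MRI response variable or threshold, so nothing is counted; the two sources of change simply cannot be told apart. Nor is the MRI analysis confined to the affected limb, since section 11.3.2 also covers body composition. The sentence quoted from section 2.4 fixes timing, not region.

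A reader might also infer that the contrast should replace the planned test. Steps 3 and 4 argue against that: a swollen limb need not shift by the same amount as a normal one, and the interval can be up to 41% wider with equal SDs. Section 4.1 does not exclude bilateral disease, and section 2.1 describes one of two earlier lymphedema patients as having recurrence in the lower extremities, in the plural. The contrast may therefore apply to a subset of unknown size.

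Finally, the contrast does not remove regression to the mean or changes in compression care in the affected limb, and it subtracts any true drug effect present in both limbs. These limits stand.

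**Conclusion.** The concern holds in a limited form. The limb-level MRI outcome has neither a control arm nor a reference limb, so a change common to both limbs cannot be separated from a limb-specific response. Under the assumed shifts of 0.2-0.5 SD, the planned test would reject in 14-56% of trials at n=20 and 11-44% at n=15 with no limb-specific effect. These rates depend wholly on the assumed shifts, because the documents give no SD or drift figure.

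The affected-minus-unaffected contrast restores 5% only for an equal absolute shift; in the proportional cases computed it reduces the error without removing it. It therefore belongs beside the planned analysis as supportive evidence. It would not by itself attribute an MRI change to propranolol. The point affects the reading of a secondary efficacy endpoint, not tolerability.

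**What to change.** Add to sections 11.3.2 and 8.4, before any Week 8 image is read:

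- In patients with one affected limb, measure the same MRI quantity in both limbs at baseline and Week 8.
- Beside the planned affected-limb change, report (a) the unaffected-limb change as a negative control and (b) the affected-minus-unaffected difference in change, one value per patient, with its confidence interval. Label both as a pre-specified supportive analysis.
- Attribute an MRI change to the affected limb only if (b) supports it.
- Report patients with bilateral disease separately and label their result as uncontrolled.

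The cost is a few sentences and extra segmentation by the same reader on scans already planned, with no new scan, patient or visit. The contrast may have a wider interval than the planned result (step 4) and a smaller n if some patients have bilateral disease. Showing (a) beside (b) lets a reader see when a change in both limbs has been subtracted.
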